**9.3.4 Tanner Staging**

This endpoint is a safety endpoint for only the OLE period of the study.

The Tanner scale (also known as the Tanner stages) is a scale of physical development in children, adolescents and adults. The scale defines physical measurements of development based on external primary and secondary sex characteristics. Subjects will be evaluated and rated as

Tanner I, Tanner II, Tanner III, Tanner IV and Tanner V. Tanner staging will occur at Screening (Visit 1), Visit 9 (Week 52) and will continue to be assessed annually for the duration of the subject's participation in the open-label phase and at the final OLE visit.

The number and percentage of subjects of each category will be summarized by Screening and OLE visit, and a listing will be provided.

### 9.3.5 Concomitant AED Levels

Concomitant AED levels are not mandatory but will be collected per sites' standard of care. A subject listing, including date and time of last AED dose and date and time of AED PK sample, will be provided.

## 10. INTERIM ANALYSES AND DATA AND MONITORING COMMITTEE (DMC)

Up to two formal interim analyses are planned, in addition to the final analysis, of treatment effect on the primary endpoint. They will be conducted when 50 subjects and 75 subjects are at least 17 weeks post randomization. The interim analyses will include only those subjects, and will be based on use of O'Brien-Fleming monitoring boundaries regarding benefit and lack of benefit. If the trial is not terminated at the interim analyses, the sample size at the final analysis will be approximately 100 participants.

(Note that while the boundaries discussed in the remainder of this section will be illustrated for the setting in which 50 (75) subjects would be at least 17 weeks post randomization at the interim analysis, these boundaries will be computed based on the actual number 'X' of subjects at the times of the interim analyses.)

In addition, two supportive analyses will be performed, for informational purposes only, at each interim analysis:

- For those subjects who stop recording measurements permanently (anticipated to be minimal in occurrence) prior to the end of the 17-week DB phase, the imputation procedure for the first sensitivity analysis described in [Section 7.1.8](#) will be applied.
- All randomized subjects who are at least 4 weeks post randomization at the time of the interim analyses will be included.

### 10.1 Termination Based on Reliable Evidence of Lack of Benefit

An O'Brien-Fleming boundary that rules out benefit will be used, protecting an experimental (one-sided) 0.025 false negative error rate, under an assumed maximum sample size of 100 participants, and under the alternative hypothesis that the percent change in 28-day seizure frequency on ganaxolone minus that on placebo truly is 0.5618 times the standard deviation for the percent change in 28-day seizure frequency; when that standard deviation is 44.5, this alternative hypothesis for the percent change in 28-day seizure frequency on ganaxolone minus

that on placebo would be 25%. (This reduction is the effect the trial has 80% power to detect at the final analysis when 100 subjects have completed their 17-week DB treatment phase.)

If the standard deviation for the percent change in 28-day seizure frequency is 44.5, then the estimate of the percent change in 28-day seizure frequency on ganaxolone minus that on placebo that would be at the boundary for early termination due to lack of benefit at 50 subjects would be approximately an estimated 10% increase, and at 75 subjects would be approximately an estimated 1% decrease.

The proposed boundary for termination based on reliable evidence of lack of benefit is somewhat conservative, in part due to the recognition that statistical significance might not be required for this trial to be sufficiently favorable to justify regulatory approval.

## 10.2 Termination Based on Definitive Evidence of Benefit

An O'Brien-Fleming boundary for definitive evidence of benefit will be used, protecting an experimental (one-sided) 0.005 false positive error rate, under an assumed maximum sample size of 100 participants, and under the null hypothesis of no effect on the percent change in 28-day seizure frequency on ganaxolone minus that on placebo.

This boundary for termination based on definitive evidence of benefit would be crossed only if the statistical strength of evidence is midway between that of one and two trials, (i.e., one in 200 under the null hypothesis), even when adjustment is made for multiplicity due to interim monitoring. It is proposed that two interim 'efficacy' analyses be performed, specifically at the times when 50% and 75% of the 100 subjects have completed the 17 week double blind period. The Z-values at the interim analyses conducted at the times of 50% and 75% information are:

$$2.64 (100/50)^{1/2} = 3.73 \quad (\text{at } 50 \text{ subjects})$$

and

$$2.64 (100/75)^{1/2} = 3.03 \quad (\text{at } 75 \text{ subjects})$$

The (one-sided) nominal p-value corresponding to the Z-value of 3.73 is 0.0001; and corresponding to the Z-value of 3.03 is 0.0012.

If the standard deviation for the percent change in 28-day seizure frequency is 44.5, then the estimate of the percent change in 28-day seizure frequency on ganaxolone minus that on placebo that would be at the boundary for early termination due to definitive evidence of benefit at 50 subjects would be an estimated 47% decrease, and at 75 subjects would be an estimated 32% decrease.

Nearly all of the experimental (one-sided) 0.025 false positive error rate will be spent at the time of the final analysis of the primary endpoint, conducted when all 100 study participants have completed their double-blind period, because the interim analyses were conducted using an O'Brien-Fleming boundary that, during the interim analyses, preserved the (one-sided) 0.005 false positive error rate. To be specific, at least  $0.0250 - 0.0013 = 0.0237$  of the (one-sided) false

positive error remains for this final analysis. Hence, the two-sided p-value at the final analysis will be approximately 0.048.

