### 7.1.2 Primary Efficacy Endpoint

The primary efficacy endpoint is the percent change from baseline in 28-day primary seizure frequency during the 17-week DB treatment phase. Primary seizure types include bilateral tonic, generalized tonic-clonic, atonic/drop, bilateral clonic, or focal to bilateral tonic-clonic seizures. Post-baseline 28-day seizure frequency will be calculated as the total number of seizures in the 17-week DB treatment phase divided by the number of days with seizure data in the phase, multiplied by 28. Baseline 28-day seizure frequency will be calculated as the total number of seizures in the baseline phase divided by the number of days with seizure data in the phase,

multiplied by 28. The calculation for percent change from baseline in 28-day seizure frequency will be done as follows for each subject:

$$\left( \frac{[(\text{Post-baseline 28-day seizure frequency}) - (\text{Baseline 28-day seizure frequency})]}{(\text{Baseline 28-day seizure frequency})} \right) \times 100\%$$

The baseline and post-baseline values and the changes and percent changes from baseline in 28-day seizure frequency will be summarized using descriptive statistics.

The difference between the treatment groups in the percent changes from baseline will be tested for statistical significance. Since the percent differences are anticipated to display skewness and/or outliers, the tests will be performed using the Wilcoxon Rank-Sum statistic.

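### The benefit boundary in SAP 10.2 does not reproduce from its stated inputs and contradicts itself at 75 subjects; one futility illustration in SAP 10.1 is about a point off

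*SAP*

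**What the plan says.** SAP 10 opens with "Up to two formal interim analyses are planned", at 50 and 75 subjects, before a final analysis at about 100. It adds that the boundaries shown are illustrations and will be computed for the actual number of subjects at each look.

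SAP 10.2 describes the benefit boundary as "protecting an experimental (one-sided) 0.005 false positive error rate", "under an assumed maximum sample size of 100 participants", with looks "specifically at the times when 50% and 75% of the 100 subjects have completed the 17 week double blind period". It then prints two Z-values: "2.64 (100/50)^{1/2} = 3.73" at 50 subjects and "2.64 (100/75)^{1/2} = 3.03" at 75. The nominal one-sided p-values given are 0.0001 and 0.0012. With a standard deviation of 44.5, the estimates at the boundary are given as decreases of 47% and 32%.

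SAP 10.1 sets an O'Brien-Fleming lack-of-benefit boundary at one-sided 0.025 against a difference of 0.5618 SD (25 points when the SD is 44.5). At 50 subjects the boundary estimate "would be approximately an estimated 10% increase"; at 75 it is given as about a 1% decrease. No Z-values are given for this boundary.

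For the primary endpoint, SAP 7.1.2 says that "the tests will be performed using the Wilcoxon Rank-Sum statistic". SAP 10 does not name the statistic used at the interims.

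**The concern.** An O'Brien-Fleming boundary is fixed by the error rate and the timing of the looks, and SAP 10.2 states both. The constant should therefore follow from them, and each printed Z and effect size should follow from the constant. Neither holds throughout. The constant does not give the stated 0.005, and the constant, Z and percentage printed for the 75-subject look imply three different thresholds.

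At stake is whether the statistician serving the Data Monitoring Committee can rebuild the rule when the looks fall at other numbers of subjects. A worked example that fails its own arithmetic leaves unclear which entry is the intended threshold.

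**Working it through.** **Inputs.** Looks at t = 0.50, 0.75 and 1.00 of 100 subjects; one-sided 0.005 for benefit (SAP 10.2) and 0.025 for lack of benefit (SAP 10.1); alternative 25 points and SD 44.5 (SAP 10.1); 1:1 allocation (SAP 1.3.1).

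**Standard errors.** SE = 44.5 × √(4/n): 12.587 at n = 50 and 10.277 at n = 75.

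**The plan's own figures.**
- 50 subjects: 2.64 × √2 = 3.734, matching 3.73. Then 3.73 × 12.587 = 46.9%, matching the 47%. The nominal p is 0.0001, as printed.
- 75 subjects: 2.64 × √(100/75) = 2.64 × 1.1547 = 3.048, so 3.05, not 3.03.
- Effect at 75: 3.03 × 10.277 = 31.1%; 3.048 × 10.277 = 31.3%. The printed 32% needs Z = 32/10.277 = 3.11.
- Nominal p at 75: 0.0012 belongs to 3.03; for 3.05 it is 0.0011.
- Interim spend: the printed 3.73 and 3.03 have a joint crossing probability of 0.00126 under the null. This agrees with the 0.0013 deducted in SAP 10.2.

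**The constant.** With Z_k = c/√t_k, c is solved so that the probability of crossing at any of the three looks equals the stated error rate (numerical integration of the joint normal distribution).

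| Rule | c | Z at 50 | Z at 75 |
|---|---|---|---|
| One-sided 0.005, looks 50/75/100 | 2.609 | 3.69 | 3.01 |
| SAP formula with 2.64 | 2.64 | 3.73 | 3.05 |

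With c = 2.64 the overall one-sided error is 0.00455. Other designs do not recover 2.64: a single interim gives 2.580 (at 50) or 2.607 (at 75), and Lan-DeMets O'Brien-Fleming-type spending gives Z of 3.80 and 3.04. Seven equally spaced looks do give 2.640, but that is not this trial.

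For c = 2.609 the effects at SD 44.5 are 3.690 × 12.587 = 46.4% and 3.013 × 10.277 = 31.0%. Nominal p-values are 0.0001 and 0.0013, and joint interim spend is about 0.0013.

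**Lack of benefit.** At one-sided 0.025 the same method gives c = 2.024. The boundary estimate is −25 + (c/√t) × SE:
- 50 subjects: −25 + 2.863 × 12.587 = +11.0% (printed: about +10%).
- 75 subjects: −25 + 2.337 × 10.277 = −1.0% (printed: about −1%).

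A rule with an interim at 50 only (c = 1.977) gives +10.2% at 50, but −1.5% at 75. On a Z scale with positive values favouring ganaxolone, the three-look limits are 25/12.587 − 2.863 = −0.88 and 25/10.277 − 2.337 = +0.10.

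**Practical effect.** With a true 30-point difference and SD 44.5, the chance that Z exceeds the limit at 50 subjects is 8.9% for 3.73 and 9.6% for 3.69. At 75 it is 45.6% for 3.03, 44.8% for 3.05 and 46.4% for 3.01.

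**The case against.** The strongest reply is that nothing here harms the trial. The SAP undertakes to protect 0.005, and 0.00455 does protect it. The interim spend agrees with the SAP's own deduction, so the allowance for the final test is unaffected. The 10% is labelled approximate, depends on an assumed SD and sits under a note that the boundaries are illustrations; the gap is one point against a standard error of 12.6. All of that stands, and it limits the weight of the point.

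Three stronger readings are tempting, and the documents do not support them.

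- *The wrong constant raises the false positive rate.* It does the opposite: 2.64 is larger than needed.
- *The same 2.64 will be carried into the boundaries at the actual numbers.* SAP 10 says only that boundaries will be computed from the actual number of subjects. Re-solving the constant is at least as natural a reading. The text should say which is meant.
- *The futility boundary is on the wrong scale and should be replaced by Wilcoxon limits of −0.88 and +0.10.* SAP 10 ties the interims to the primary endpoint, whose test is Wilcoxon, so what is missing is the name of the statistic. Those two values come from the mean-difference statistic under a normal shift. In a simulation of a 25-point shift (SD 44.5) at 50 subjects, the mean Wilcoxon Z was 1.87 for normal data and 2.52 for log-normal data (log-SD 0.6, an assumed shape), against 1.99 for the mean-difference statistic. They are not exact Wilcoxon limits under the skewness the SAP expects.

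The reply does not remove the inconsistency at 75 subjects, which needs only multiplication to see.

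**Conclusion.** The point holds as a correction of stated stopping thresholds, with low practical weight. The benefit constant for the stated design is 2.609 rather than 2.64, a conservative difference (0.0046 against 0.005). At 75 subjects the constant, Z-value and percentage imply thresholds of 3.05, 3.03 and 3.11. The futility illustration at 50 subjects should be about 11%; this is the weakest part, because the figure is offered as approximate.

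The contradiction between 2.64 and 3.03 rests on no assumption. The percentages rest on the SAP's SD of 44.5 and 1:1 allocation. The constants rest on the classical O'Brien-Fleming form that the SAP's formula uses, with information proportional to the number of subjects.

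**What to change.** In SAP 10.2, choose one of two repairs.

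1. Use 2.61: Z of 3.69 and 3.01, nominal one-sided p of 0.0001 and 0.0013, and decreases of 46% and 31% at SD 44.5. The cost is a slightly lower bar for stopping for benefit, with interim spend rising from 0.00126 to about 0.0013. The 0.0013 deducted before the final test should be rechecked: it holds to four decimals as a joint probability, while adding the two nominal p-values gives 0.0001 + 0.0013 = 0.0014.
2. Keep 2.64 and describe it as deliberately conservative. Correct 3.03 to 3.05, its nominal p from 0.0012 to 0.0011, and 32% to 31%. The cost is a slightly stricter limit at 75 subjects than the one now printed.

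Under either choice, change the futility illustration at 50 subjects in SAP 10.1 from 10% to 11%, and state in SAP 10 that the constant is re-solved at the actual information fractions.

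As a secondary clarification, name the standardised Wilcoxon statistic as the interim statistic. If the futility limits are then put on a Z scale, label −0.88 and +0.10 as normal-shift approximations. These are text changes only and should be made before any unblinded look.

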### 7.1 Double-Blind Phase

All efficacy analyses will be conducted in the ITT population. A supportive analysis of the primary and secondary efficacy endpoints also will be conducted in the PP population.

The estimand that is most clinically relevant as well as estimable in a manner that protects the integrity of randomization is the outcome measure (e.g., the percent change in 28-day seizure frequency), where ALL randomized subjects would be included in this analysis throughout the study period. Hence, all available data will be used, even if they were collected after the subject stopped taking study medication, regardless of whether the subject took rescue medication. [Section 7.1.1](#) details the handling of missing data.

For the analyses of seizures, the baseline phase consists of 6 weeks before the first day of treatment and the DB phase starts the day following the first day of DB treatment until the final visit for subjects who do not enter the OLE and up to the day before the first dose of OLE treatment for those who do. The first day of treatment is not in either phase since the seizures could occur both before and after the first treatment.

Tests of significance between the 2 treatment groups will be performed for the primary endpoint with a 2-sided significance level of 0.05.

Seizure diary compliance for the baseline and the post-baseline DB phase intervals will be calculated as:

$100 \times (\text{Number of Days with Available Seizure Diary}) / (\text{Last Available Seizure Diary Date} - \text{First Day of the Phase} + 1)$ .

Seizure diary compliance between visits will be calculated as:

$100 \times (\text{Number of days with available seizure data between visits}) / \text{Number of days between visits}$ , with the days between visits defined as the day of the prior visit up to the day before the current visit.

The compliances will be summarized with descriptive statistics and the percentage of subjects at least 80% compliant.

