## 11. SUMMARY OF MAJOR CHANGES IN THE PLANNED ANALYSES

Any major changes in the planned analyses will appear in updated versions of this SAP. In the event of discrepancies between the SAP and the protocol, the SAP will take precedence.

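### SAP 10.2 miscalculates its illustrative 75-subject efficacy boundary (3.05 and 31%, not 3.03 and 32%), and the SAP does not say in one place what level the final primary test uses

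*SAP*

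**What the plan says.** SAP 10 plans a 50-subject and a 75-subject look: "Up to two formal interim analyses are planned, in addition to the final analysis". SAP 10.2 uses an O'Brien-Fleming efficacy boundary at one-sided 0.005 with constant 2.64. For the second look it prints "2.64 (100/75)^{1/2} = 3.03", a nominal one-sided p of 0.0012 and, at SD 44.5, a boundary effect that "at 75 subjects would be an estimated 32% decrease". SAP 10 adds that "these boundaries will be computed based on the actual number 'X' of subjects at the times of the interim analyses".

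On the final analysis, SAP 10.2 states: "Nearly all of the experimental (one-sided) 0.025 false positive error rate will be spent at the time of the final analysis". It subtracts 0.0013 of interim spend from 0.0250, says that at least 0.0237 remains, and concludes: "Hence, the two-sided p-value at the final analysis will be approximately 0.048".

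SAP 7.1 states: "Tests of significance between the 2 treatment groups will be performed for the primary endpoint with a 2-sided significance level of 0.05". It does not refer to section 10. SAP 7.1.2 names the Wilcoxon rank-sum test without a level. SAP 7.1.7 says no multiplicity protection is needed and does not mention the interim looks. Protocol 9.7.1 also gives 0.05, but Protocol 9.11 leaves the interim analysis to the SAP, and SAP 11 says: "In the event of discrepancies between the SAP and the protocol, the SAP will take precedence".

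**The concern.** There are two separate defects.

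1. A printed stopping threshold does not follow from the formula printed beside it, and the slip runs on into the interim spend and the remainder.
2. The trial has one inferential test, and its final threshold should be stated once, as a definite number, before unblinding. Someone working from section 7 alone would apply 0.05; someone working from 10.2 would apply about 0.048. A final p of 0.049 passes one and fails the other. SAP 11 ranks the SAP above the protocol, not one SAP section above another. If the result fell in that gap, a choice made after unblinding would be hard to defend.

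**Working it through.** **Inputs.** Constant 2.64, looks at 50 and 75 of 100 subjects, SD 44.5, overall one-sided 0.025 (SAP 10 and 10.2); 1:1 allocation and N = 100 (SAP 1.3.2).

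**Formulas.** Boundary Z = 2.64 × √(100/n). Standard error = 44.5 × √(4/n), which is 12.587 at n = 50, 10.277 at 75 and 8.900 at 100. Boundary effect = Z × SE.

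**50-subject line (reproduces).** 2.64 × √2 = 3.7335, printed 3.73. Effect 3.7335 × 12.587 = 47.0%, printed 47%. Nominal one-sided p 0.000094, printed 0.0001.

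**75-subject line (does not).** 2.64 × √(100/75) = 3.0484, printed 3.03. Effect 3.0484 × 10.277 = 31.3%, printed 32%. The printed 3.03 also gives 31%: 3.03 × 10.277 = 31.1%. A 32% effect would need Z = 32/10.277 = 3.11.

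The exact O'Brien-Fleming constant, Lan-DeMets spending, a constant of 2.62, a 37/38 split and t quantiles were also tried. None gives the full printed set. For example, 2.62 gives 3.03 at 75 subjects but 3.71 at 50, and t quantiles give 32.3% at 75 but about 51% at 50.

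**Nominal p at 75 subjects.** One-sided p is 0.00122 at Z = 3.03, 0.00115 at the unrounded 3.0484, and 0.00114 at 3.05. Beside a printed 3.05 the four-place value is therefore 0.0011.

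**Interim spend carried through.**

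| | Printed | Corrected |
|---|---|---|
| Sum of nominal p-values | 0.0001 + 0.0012 = 0.0013 | 0.0001 + 0.0011 = 0.0012 |
| Remainder of 0.0250 | 0.0237 | 0.0238 |
| Doubled | 0.0474 | 0.0476 |

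The printed remainder doubles to 0.0474, which rounds to 0.047. The corrected one doubles to 0.0476 and agrees with the stated 0.048.

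**Effect of the choice of final level.** Joint calculation over the correlated looks, constant 2.64, efficacy boundaries only (lack-of-benefit boundary treated as non-binding):

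| Looks taken | Total one-sided error, final at 0.05 | Final at 0.048 | Two-sided final level that keeps 0.025 |
|---|---|---|---|
| Both | 0.02506 | 0.02406 | 0.0499 |
| 75 only | 0.02505 | 0.02405 | 0.0499 |
| 50 only | 0.02501 | 0.02401 | 0.04998 |
| None | 0.02500 | 0.02400 | 0.0500 |

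Power for a 25% difference, Φ(25/8.9 − Z): 80.2% at Z = 1.960 (0.05) and 79.7% at Z = 1.977 (0.048).

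Ignoring early stopping, the chance of a favorable final p between 0.048 and 0.05 is (0.05 − 0.048)/2 = 0.1% under the null and 80.2% − 79.7% = 0.5% at a 25% effect.

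**Does the final threshold in SAP 1.3.2 settle the level?** No. It is 1.960 × 8.9 = 17.44 at 0.05 and 1.977 × 8.9 = 17.60 at 0.048. Both fit the stated approximate 17.5%.

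**The case against.** The strongest reply is that SAP 7.1 and 10.2 do not conflict. Two-sided 0.05 is the overall level, equal to the one-sided 0.025 from which 10.2 starts, and 10.2, as the specific section, then derives the level for the last look. That is the natural reading. A reader might infer a flat contradiction over the primary test, but the documents do not support that. What stands is narrower: 7.1 attaches 0.05 to the test itself without pointing to section 10, and 10.2 gives only an approximate level.

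A reader might also infer that 0.048 fails if fewer than two looks are taken. It does not: 10.2 presents 0.0237 as a minimum, and fewer looks spend less. The section simply does not say that the same level then applies.

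Nor is the protocol in conflict. It prints 0.05, but it defers to the SAP on the interim analysis, and the SAP takes precedence.

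Finally, the 75-subject figures do not themselves set a stopping decision, because SAP 10 recomputes the boundaries from actual counts. That limits the consequence; the printed equation is still wrong.

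**Conclusion.** The point holds as a minor one. The 75-subject line is wrong on its own formula: 3.05 and 31%, not 3.03 and 32%. The final level is inferable but is not stated as one definite rule.

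A reader might take this to mean that the type I error is inflated. The figures do not support that in any material sense: even at 0.05 after both looks, total one-sided error is 0.0251, and 0.048 is conservative at 0.0241.

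These results assume looks at exactly 50 and 75 subjects, normally distributed test statistics, a non-binding lack-of-benefit boundary and, for effects and power, SD 44.5. They use the SAP's difference-in-means approximation rather than the Wilcoxon test itself. The 3.05 rests on the SAP's constant of 2.64. The exact three-look constant is 2.61, which gives 3.01 at 75 subjects, so 2.64 is slightly conservative; the 31% holds with either.

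**What to change.** In SAP 10.2:

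- Change 3.03 to 3.05 in both places, and the matching nominal one-sided p from 0.0012 to 0.0011 (0.00115 at the unrounded Z of 3.048). Changing Z alone would leave a p-value that does not match it.
- Change 32% to 31%.
- Change the interim spend from 0.0013 to about 0.0012 and the remainder from 0.0237 to about 0.0238.
- Replace the approximate level with a fixed two-sided 0.048 that applies whether two, one or no interim looks are taken. The joint calculation supports this as conservative, although 0.048 is slightly above the 0.0476 from simple subtraction.

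In SAP 7.1, state that 0.05 is the overall two-sided level and that the final analysis is tested at the level in section 10.2.

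The cost is SAP wording only, with no added patients or data. Relative to testing at 0.05, the fixed 0.048 gives up about half a percentage point of power at a 25% difference.
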